### 8.2. Response Evaluable Population

Response evaluable population includes all enrolled subjects who satisfy all of the following conditions. Two sets of criteria are defined for the 2nd condition and hence two response

evaluable populations will be defined: (a) is the original definition per protocol, used in statistical outputs (unless specified otherwise) and (b) is the alternative definition used in exploratory efficacy analysis as described in the CSR. To differentiate the two definitions in the outputs the population line in the TLFs will be “Response Evaluable Population” for definition (a) and “Response Evaluable Population (Alternative Definition)” for definition (b).

1. Have measurable disease and assessment at baseline (for inclusion in expansion cohorts, subjects also need to meet the appropriate protocol criteria for genetically-defined tumor)
2. Two sets of criteria are defined below (a or b) based on the dosing information
  - a. Received at least 75% of 1 cycle of study medication, OR
  - b. An alternative definition might be used for some exploratory efficacy analysis:  
Received at least 75% of cycle 1 study medication at  $\geq 300$  mg or continued on-study after 2 cycles of treatment at any dose level.
3. Have at least one post-baseline disease assessment OR discontinued treatment due to adverse event or disease progression or death

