## 11.2. Time to Progression (TTP)

Time to progression is defined as time from the Cycle 1 Day 1 to the earliest date of radiographic disease progression per RECIST 1.1. If a subject did not experience progressive disease, TTP is censored at the last imaging assessment. TTP will be analyzed using the Kaplan-Meier method. The output will include count and percentage of subjects with events or censored outcome including the type of event and censoring. Median TTP and 95% CI based on log-log

transformation will be provided. Landmark analyses at various timepoints may be carried out if of clinical interest. Kaplan-Meier plot supporting the table summary may also be generated.

In addition to TTP by RECIST 1.1 criteria based only on the radiographic assessments, a second definition of TTP which incorporates the clinical progression will be used. The clinical progression is based on the medical review of the reasons of treatment discontinuation or study continuation. If a subject is considered having clinical progression the date of treatment or study discontinuation will be used as date of clinical progression and the TTP is defined as time from Cycle 1 Day 1 to the earliest date of clinical or radiographic disease progression.

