### 11.3. Progression-free Survival (PFS)

Progression-free survival is defined as time from Cycle 1 Day 1 to the earliest date of radiographic disease progression per RECIST 1.1 or death, whichever happens first. The detailed event and censoring rules are shown in the table below following the hierarchical order of the logic:

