**Table 4: Event and Censoring Rules for PFS**

Situation	Date of Progression or Censoring	Outcome
Death or progression after more than 1 missed imaging visit	Date of last adequate assessment before missed visits	Censored
Death or progression without more than 1 missed visit	Earliest date of death or progression	Event
No Death or progression	Date of last imaging assessment	Censored
No post-baseline assessment	Date of Cycle 1 Day 1	Censored

PFS will be analyzed using the Kaplan-Meier method. The output will include count and percentage of subjects with events or censored outcome including the type of event and censoring. Median PFS and 95% CI based on log-log transformation will be provided. Landmark analyses at various timepoints may be carried out if of clinical interest. Kaplan-Meier plot supporting the table summary may also be generated.

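### SAP Table 4 never reaches its Day 1 censoring row, and PFS has no version that counts clinical progression, so unscanned early failures drop out of the curve

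*SAP*

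**What the plan says.** **PFS events.** SAP Section 11.3: "Progression-free survival is defined as time from Cycle 1 Day 1 to the earliest date of radiographic disease progression per RECIST 1.1 or death". Clinical progression without imaging is not an event.

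**Order of the rules.** The same section: "The detailed event and censoring rules are shown in the table below following the hierarchical order of the logic". Table 4 then has four rows:

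1. "Death or progression after more than 1 missed imaging visit": censored at the last adequate assessment before the gap.
2. "Death or progression without more than 1 missed visit": event.
3. Neither death nor progression: censored at the most recent imaging date. The row does not require that imaging to be post-baseline.
4. "No post-baseline assessment": censored at Cycle 1 Day 1.

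**Who is analysed.** All efficacy analyses use the Response Evaluable Population unless stated otherwise. Under SAP Section 8.2 a subject needs measurable disease and an assessment at baseline, at least 75% of one cycle of drug, and, as condition 3, "Have at least one post-baseline disease assessment OR discontinued treatment due to adverse event or disease progression or death". Subjects with no post-baseline scan are therefore included by design. Protocol Section 11.1.2 classes those who progress, become intolerant or die before a scan as nonresponders.

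**TTP.** SAP Section 11.2 censors subjects without radiographic progression at their last imaging and has no rule for subjects never scanned after baseline. It then adds that "a second definition of TTP which incorporates the clinical progression will be used", dated at treatment or study discontinuation. The output list has a table and a plot for that version (Table 14.2.2.2, Figure 14.2.1.3). PFS appears only per RECIST (Table 14.2.2.3, Figure 14.2.1.4).

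**The concern.** Two separate things look wrong.

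First, Table 4 contains a rule for subjects with no scan after baseline, but its place in the order appears to disable it. The subjects it was written for then get a censoring date before the time origin.

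Second, the subjects admitted through the second half of condition 3 include some of the fastest failures. They stay in the ORR denominator as failures, but a subject who stopped for clinical progression, was never rescanned and has no recorded death counts in PFS as neither an event nor follow-up. Censoring tied to rapid decline is informative, and it lengthens the curve.

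PFS is one of the efficacy endpoints listed under a primary objective. TTP with clinical progression could also come out shorter than the reported PFS, although PFS has death as an additional event.

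**Working it through.** The plan states no PFS median, event count or power, so there is no figure to reproduce. Two checks apply.

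**Check 1: run Table 4 in its stated order.** Classify subjects by death or progression (yes/no), more than one missed imaging visit (yes/no) and any post-baseline scan (yes/no), giving 8 combinations.

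| Death or progression | >1 missed visit | Post-baseline scan | Row reached |
|---|---|---|---|
| Yes | Yes | Yes or no | 1 |
| Yes | No | Yes or no | 2 |
| No | Yes or no | Yes or no | 3 |

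None of the 8 reaches row 4. For a subject without a post-baseline scan:

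- No recorded death: row 3, so the only imaging date is the baseline scan. Protocol Section 7.6 (note f) allows that scan up to 35 days before Cycle 1 Day 1. With a scan 14 days before, the date difference is −14 days. If the duration convention in SAP Section 9.3.2 (later minus earlier plus 1) is applied literally, it becomes 14 + 1 = +15 days, which is also meaningless.
- Death with no more than one missed visit: row 2, an event.
- Death after more than one missed visit: row 1, where the last adequate assessment is again the baseline scan.

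If row 4 is tested before row 3, the two combinations with no death or progression and no post-baseline scan go to Day 1 and the other six are unchanged. The late death in row 1 still carries the baseline date.

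**Check 2: effect on the PFS curve.** Inputs:

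- First scan due at 8 weeks ± 1 (Protocol Section 7.2.2).
- Entry to the population at 75% of a cycle, which is 0.75 × 28 = 21 daily doses on the continuous schedule.
- Assumption: a share f stops for clinical progression, uniformly between days 21 and 56, with no scan and no death recorded.
- Assumption: the others have exponential PFS with median M. M = 3 to 4 months borrows the figure in Protocol Section 2.2.2 for platinum-resistant ovarian cancer.

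A subject censored at or before Day 1 leaves the risk set before the first event, so the reported curve is that of the others:

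- S_others(t) = 2^(−t/M)

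With clinical progression counted as an event, after day 56:

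- S(t) = (1 − f) × 2^(−t/M), with median M × log2[(1 − f)/0.5]

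For M = 3.5 × 30.4375 = 106.5 days:

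- S_others(112) = 2^(−112/106.5) = 0.48
- f = 10%: S(112) = 0.9 × 0.4825 = 0.43; median = 106.5 × log2(1.8) = 90 days
- f = 20%: S(112) = 0.8 × 0.4825 = 0.39; median = 106.5 × log2(1.6) = 72 days

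A simulation of 100,000 subjects agrees:

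| f | Median, censored at Day 1 | Median, counted as event | Overstatement | 16-week PFS, censored vs event |
|---|---|---|---|---|
| 5% | 107 d | 99 d | 8 d = 0.3 mo | 0.48 vs 0.46 |
| 10% | 107 d | 90 d | 17 d = 0.6 mo | 0.48 vs 0.43 |
| 20% | 107 d | 72 d | 35 d = 1.2 mo | 0.48 vs 0.39 |
| 30% | 107 d | 55 d | 52 d = 1.7 mo | 0.48 vs 0.34 |

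For M between 3 and 4 months the overstatement is 0.2–0.3, 0.5–0.6, 1.0–1.3 and 1.3–2.1 months at the four shares.

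Two qualifications come from the same runs:

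- Censoring at a baseline scan 14 days before Day 1, instead of at Day 1, changes the median by at most about 1 day. Row order is not the source of the bias.
- When the others' progression is dated at 8-weekly scans, the median moves only in whole 56-day steps. At M = 3.5 months it stays at 112 days for f = 5%, 10% and 20% and falls to 56 days at 30%. At M = 4 months the step (168 to 112 days) comes at 10%. The 16-week PFS shifts throughout.

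**The case against.** **Radiographic PFS is a declared choice.** Appendix 2 of the protocol says symptomatic deterioration is a reason for stopping therapy and does not describe objective response. The second TTP definition already shows part of the effect, OS is reported, the PFS table will show types of event and censoring, and SAP Section 9.1.2 calls all confidence intervals supportive. This stands. It is why RECIST PFS should remain the main analysis and the addition is a sensitivity analysis.

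**Many of these subjects are recovered.** An early death is an event under row 2. Protocol Section 7.3 asks for imaging at the safety follow-up visit, 30 ± 7 days after the last dose, unless progression was already on a scan or a scan was done within 6 weeks. After 21 daily doses the earliest normally timed visit is about day 21 + 23 = 44, so a baseline scan cannot meet that exemption. This also stands, in part: the visit's investigations are to be done where possible, assessments stop once new anticancer therapy starts (Section 7.6, note m), and survival updates are collected as needed (Section 7.4).

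**The intended date is obvious.** A programmer would probably use Day 1. That is likely, and the effect on the estimate is negligible. But the order is stated explicitly, and TTP has no such row to fall back on.

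**Stronger readings that a reader might infer.** The documents do not support these:

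- That the row order makes PFS too long. It does not; the bias comes from leaving clinical progression out of the events.
- That all rapid failures are lost. Only those with no scan and no timely recorded death are.
- That DOR suffers too, because it borrows Table 4. A confirmed responder has post-baseline scans, so the no-scan case cannot arise. Duration of stable disease borrows the table but is only listed.
- That PFS is inflated by a known amount. Neither the share nor the median comes from this trial's plan.

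**Conclusion.** Two findings hold, with different weight.

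1. **Wrong as written, with little numerical effect.** Rows 1 to 3 of Table 4 are exhaustive, so row 4 cannot apply. Subjects with only a baseline scan and no death get zero or negative PFS time. Late unscanned deaths in row 1, and unscanned subjects in RECIST TTP, have the same problem.
2. **A cheap improvement that addresses a real bias.** Subjects kept by SAP Section 8.2 after stopping for progression without a scan, and with no timely death or follow-up scan, contribute nothing to PFS. The direction is upward if they fail earlier than the rest, as is to be expected.

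The size is unknown because the share is unknown. The 0.3 to 1.7 months applies to assumed shares of 5% to 30%, an exponential 3.5-month median in the others, continuous progression dates and no recovery by scan or death. With 8-weekly dating, a 5% share moved the median in none of the three scenarios (3, 3.5 and 4 months).

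**What to change.** **(a) Table 4.**
- Before row 3, test for no post-baseline assessment and no death, and censor at Cycle 1 Day 1.
- Limit row 3 to post-baseline imaging.
- In row 1, censor at Cycle 1 Day 1 when there is no adequate post-baseline assessment. Moving row 4 alone would leave this case unresolved.

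**(b) TTP.** Censor any subject with no post-baseline imaging and no progression event at Cycle 1 Day 1, whether or not the subject died. Death is not a TTP event, so a condition on being alive would leave unscanned deaths at the baseline date.

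**(c) Sensitivity analysis.** Keep RECIST PFS as the main analysis. Add PFS counting clinical progression, dated as in the second TTP definition, with a table and Kaplan-Meier plot beside Table 14.2.2.3. Report how many subjects are censored at Day 1, by reason, so that the reader can see the share.

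**Cost.** A few lines of rule text, one table and one figure. Clinical progression is less objective in an open-label trial, which is why this version should sit beside RECIST PFS and not replace it.

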### 11.4. Overall Survival (OS)

Overall survival is defined as time from the Cycle 1 Day 1 to the date of death. If a subject doesn't have a recorded death in the database, OS will be censored at the date at which the subject is last known to be alive. The last known alive date is based on searching the last date from the following CRF forms:

- Treatment start and end date from the continuous dosing page
- Treatment start date from the first dose page
- Date of off-treatment

- Date of follow-up or date of death from the follow-up page
- Date of visits

OS will be analyzed using the Kaplan-Meier method. The output will include count and percentage of subjects with death or censored outcome. Median OS and 95% CI based on log-log transformation will be provided. Landmark analyses at various timepoints may be carried out if of clinical interest. Kaplan-Meier plot supporting the table summary may also be generated.

## 12. SAFETY ANALYSIS

All safety analyses will be based on the safety evaluable population.

### 12.1. Extent of Exposure and Compliance

Duration of treatment is defined as from the date of first dose in the treatment phase to the date of last dose taken from the SEA737 drug administration CRF page. If a subject only received the first dose for PK, the duration of treatment will be set to 1 day. In addition to the numeric summary of duration of treatment, the count and percentage of the following intervals will be presented:

- $\geq 4$  weeks
- $\geq 8$  weeks
- $\geq 12$  weeks
- $\geq 16$  weeks
- $\geq 20$  weeks

Cycle 1 compliance is used as part of the definition of the response evaluable population and will be summarized as numeric result and categorical result ( $\geq 75\%$  and  $< 75\%$ ). Cycle 1 compliance is from the SRA737 drug administration form for both QD and BID frequencies. For subject without compliance information on the CRF, the compliance will be calculated as follows:

Compliance = (Cycle 1 last dose date - first dose date + 1 - days when dose was not given) / 28  
 \*100%

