3.8 SUBJECT EVALUABILITY

3.8.1 *DLT EVALUABLE*

All subjects receiving at least 75% of planned doses of SRA737 within Cycle 1 and those subjects receiving less than these planned doses of SRA737 due to DLT will be considered evaluable for dose review decisions.

3.8.2 *REPLACEMENT OF SUBJECTS*

In the Dose Escalation Phase, if agreed by the sponsor, subjects will be replaced if they receive less than 75% of planned doses of SRA737 during the DLT period for reasons other than drug-related toxicity.

In the Cohort Expansion Phase, subjects who are not response-evaluable may be replaced in order to achieve 20 response-evaluable prospectively-selected genetically-defined subjects per indication- specific expansion cohort.

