5.2 ALTERNATIVE DOSING REGIMEN

Consideration may be given to alternative dosing schedules at any time during the study, following discussion between the Sponsor and investigators. It may be more likely that an alternative schedule will be needed if the C_{min} at the MTD of SRA737 is less than 100 nM (the concentration below which sustained Chk1 inhibition is not anticipated), and/or if safety and tolerability data, PK and/or PDn data (eg, time to onset and time to recovery of myelosuppression) indicate that an alternative dosing schedule would be more suitable. Alternative schedules may include, but are not limited to, the following examples: 5 days of dosing followed by 2 days of non-dosing each week; 1 week of daily dosing followed by 1, 2, or 3 weeks of non-dosing; 2 or 3 weeks of daily dosing followed by 1, or 2 weeks of non-

dosing; or twice daily dosing. Alternative dosing schedule cohorts may be recruited in parallel to or instead of the continuous schedule cohorts.

The initial starting dose for an alternate schedule will depend on the safety, tolerability and PK results from the previous schedule cohorts. If an alternative schedule is to be tested after an MTD has been identified with the previous schedule, the starting total weekly dose for the new schedule will not exceed the total weekly dose at the MTD for the previous schedules. If an MTD has not been identified with the previous schedule, a dose escalation step may occur; however, the dose escalation may not exceed 50% based on the total weekly dose.

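### The fallback for missing Cycle 1 compliance divides by a fixed 28 days, so full adherence on some of the protocol's example intermittent schedules scores below the 75% gate

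*SAP*

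**What the plan says.** SAP 12.1 takes the value from the case report form by default: "Cycle 1 compliance is from the SRA737 drug administration form for both QD and BID frequencies". The formula is a fallback: "For subject without compliance information on the CRF, the compliance will be calculated as follows". It reads "Compliance = (Cycle 1 last dose date - first dose date + 1 - days when dose was not given) / 28", times 100%. Nothing in SAP 12.1 changes the 28 by schedule or says whether a planned rest day counts as a day without a dose.

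The value has a consequence: "Cycle 1 compliance is used as part of the definition of the response evaluable population". SAP 8.2 sets the dosing condition of definition (a) as "Received at least 75% of 1 cycle of study medication", and SAP 11 makes that population the default for every efficacy analysis.

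Protocol 5.2 names alternative regimens as examples, among them "5 days of dosing followed by 2 days of non-dosing each week", patterns of one to three weeks on with one to three weeks off, and twice-daily dosing. SAP 3.2 keeps alternative schedules in scope. For DLT evaluability, Protocol 3.8.1 uses a planned-dose basis: "All subjects receiving at least 75% of planned doses of SRA737 within Cycle 1".

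**The concern.** A compliance measure should compare what was taken with what was prescribed. The fallback compares it with the calendar. On an intermittent schedule, rest weeks after the last dose of the cycle never enter the numerator but stay in the denominator. Rest days between doses may also be subtracted, depending on how the formula is read. A subject who followed the prescription exactly can then be scored as non-compliant and removed from the set used for best overall response, TTP, PFS and OS. Whether that happens would depend on the assigned schedule and on whether a CRF field was filled in, not on adherence. The same score would also misstate compliance in the exposure table (14.3.1).

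**Working it through.** **Inputs.** The formula and fallback condition come from SAP 12.1, the 75% threshold from SAP 8.2 and 12.1 (exactly 75% qualifies), and the eight intermittent patterns from Protocol 5.2. Protocol 5.1 sets a 28-day cycle for continuous treatment. No cycle length is stated for the alternatives, so 28 days is assumed here and varied below. The first dose is taken to fall on Cycle 1 Day 1. The plan states no compliance result to reproduce.

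**Check on the intended case.** Continuous daily dosing with no missed day gives (28 − 1 + 1 − 0)/28 = 100%, so the formula is correct there.

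**Two readings of the subtracted days.**
- Literal: every undosed day between first and last dose is subtracted, so the score is dosing days/28.
- Missed only: planned off-days are not subtracted, so with full adherence the score is (last dosing day − first dosing day + 1)/28.

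**Full adherence in a 28-day cycle:**

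| Schedule (on/off) | Planned dosing days | Last dosing day | Literal | Missed only |
|---|---|---|---|---|
| 5 days/2 days | 20 | 26 | 20/28 = 71.4% | 26/28 = 92.9% |
| 1 week/1 week | 14 | 21 | 14/28 = 50.0% | 21/28 = 75.0% |
| 1 week/2 weeks | 14 | 28 | 14/28 = 50.0% | 28/28 = 100% |
| 1 week/3 weeks | 7 | 7 | 7/28 = 25.0% | 7/28 = 25.0% |
| 2 weeks/1 week | 21 | 28 | 21/28 = 75.0% | 28/28 = 100% |
| 2 weeks/2 weeks | 14 | 14 | 14/28 = 50.0% | 14/28 = 50.0% |
| 3 weeks/1 week | 21 | 21 | 21/28 = 75.0% | 21/28 = 75.0% |
| 3 weeks/2 weeks | 21 | 21 | 21/28 = 75.0% | 21/28 = 75.0% |

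On the literal reading five of the eight patterns fail and three sit exactly on the threshold. On the missed-only reading two fail: 1/3 and 2/2.

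**One missed dose, literal reading.** On 2/1, 3/1 or 3/2 the score falls to 20/28 = 71.4%, a fail, although 20/21 = 95.2% of planned doses were taken.

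**Cycle length.** If a cycle is instead one on-block plus one off-block, the two readings agree, because no rest days fall between doses. Then 1/1, 1/2 and 1/3 score 7/28 = 25%, 2/1 and 2/2 score 14/28 = 50%, and 3/1 and 3/2 score 21/28 = 75%. The 1/3 and 2/2 patterns are 28 days long either way, so their failure does not depend on this assumption.

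**Planned days as denominator.** Every fully adherent subject scores 100%. One missed dose gives 19/20 = 95.0% (5/2), 13/14 = 92.9% (1/1, 1/2, 2/2), 6/7 = 85.7% (1/3) or 20/21 = 95.2% (2/1, 3/1, 3/2). Continuous daily dosing stays at 28/28.

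**Twice-daily dosing.** The formula counts days. A subject who took one of two doses on all 28 days took 28/56 = 50% of planned doses but scores 28/28 = 100%.

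**The case against.** The best defence is that the formula was written for the dosing that took place. The SAP shows knowledge of the data: its Table 1 reproduces misspelled database terms, and SAP 13 reports items that were not collected. Where it describes dosing it names once-daily and twice-daily frequencies and a continuous dosing page, with no display group for an intermittent schedule. For daily dosing, 28 dosing days is the correct denominator. The formula also applies only when the CRF value is absent. The planned-dose wording in Protocol 3.8.1 belongs to DLT evaluability; the response evaluable rule in Protocol 11.1.2 speaks of 75% of a cycle of medication. Any exclusion would be visible in Table 14.1.4 and Listings 16.2.1.7 and 16.2.3.1. SAP 9.1.2 treats all confidence intervals as supportive.

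Most of this stands, and it limits reach. The documents do not show that any subject received an intermittent schedule. They do not exclude it either, since Protocol 5.2 and SAP 3.2 both permit it, and a rule that gates the efficacy set should be right for every regimen in scope. Listing an exclusion makes it visible but does not correct it.

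A reader might infer that adherent subjects on the intermittent schedules generally drop out of the efficacy population. The documents do not support that. In a 28-day cycle, full adherence on 2/1, 3/1 and 3/2 meets the threshold. The failures of 5/2, 1/1 and 1/2 depend on counting planned off-days as days not given, which SAP 12.1 does not state. Subjects with a CRF value are untouched. Definition (b) in SAP 8.2, which is exploratory, can retain subjects still on study after two cycles. The twice-daily problem runs the other way, towards wrongful inclusion.

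**Conclusion.** Wrong as written, low reach. The fixed denominator fails fully adherent subjects on 1 week on/3 off (25%) and 2 weeks on/2 off (50%) under both readings. The literal reading adds 5/2 (71.4%), 1/1 (50%) and 1/2 (50%), and leaves 2/1, 3/1 and 3/2 one missed dose from exclusion. Because the reading is unstated, two programmers could score the same adherent 5/2 subject at 71.4% or 92.9%, on opposite sides of the gate. Apart from 1/3 and 2/2, the figures rest on the assumed 28-day cycle.

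The effect on ORR cannot be sized, because the documents give neither the number of subjects on such schedules nor the number with missing CRF compliance. As illustration only, with a cohort of 20, wrongly dropping one responder of three moves 3/20 = 15.0% to 2/19 = 10.5%, and dropping one non-responder moves it to 3/19 = 15.8%.

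**What to change.** In SAP 12.1, define fallback compliance as dosing days taken in Cycle 1 divided by dosing days planned in Cycle 1 for the assigned schedule, times 100%. State that planned off-days are not missed doses, and state the Cycle 1 length used for each alternative schedule. For twice-daily dosing, count doses rather than days where individual doses are recorded; the documents do not show that such records exist when the CRF compliance field is empty, so this part is conditional. Continuous once-daily dosing keeps its denominator of 28 and its results do not change.

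The cost is a short change of SAP wording and one derivation. The day-based version needs only each subject's assigned schedule in addition to the dates and undosed days that the formula already uses.
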